### Tumour Response Evaluation

Will be measured at Week 12 (3 months post randomisation) using the Response Evaluation Criteria in Solid Tumours (RECIST) guidelines as recommended by the NCI (Appendix 3). Following this evaluation, the Tumour Response Evaluation CRF should be completed indicating the response status of the patient's disease **within the irradiated field**. If there is evidence of disease progression **within the irradiated field** then the Disease Progression Form should be completed. Distant progression does not need to be reported. However any subsequent treatment for lymphoma at any anatomical site should be recorded.

#### Overall Survival

Data will be collected until the time of death, upon which the Patient Death CRF should be completed.

### 3.9 Procedures for assessing safety

Acute toxicity will be determined at 4 weeks post randomisation using the RTOG Acute Radiation Morbidity Scoring Schema (Appendix 2). The late toxicity will then be assessed at every visit thereafter using the RTOG/EORTC Late Radiation Morbidity Scoring Schema (Appendix 2). See section 6 on Safety Reporting for more information.

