#### Trial interventions – research and control

Patients will be randomised to receive either 4Gy in 2 fractions (experimental arm) over the course of 2 consecutive days or 24Gy in 12 fractions (control) over 16 days, treating daily Monday to Friday. Involved field radiotherapy will be given based on the tumour mass rather than anatomical regions. Recently published data has shown a high level of durable response with only 4Gy in 2 fractions.

For more details refer to section 3.

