#### **Duration**

Patients in the experimental arm (4Gy) will receive treatment over 2 consecutive days while those in the control arm (24 Gy) will be treated for 16 days on a Monday to Friday basis.

[figure not shown]
All patient follow up visits are calculated from the date of randomisation. Patients will be reviewed at 4 weeks, 12 weeks and 6 months post randomisation, then every 6 months until 2 years post randomisation. They will then be reviewed annually until they are 5 years post randomisation for assessment of late toxicity. Subsequently patients will be reviewed annually for monitoring of overall survival.

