# 1.6 Rationale and objectives

No systematic review has been identified in the Cochrane, Medline or Pub Med databases. No trials addressing this question are listed on the ICRP website or on the NCI PDQ trials database. A search of CancerLit, Medline and the Cochrane Database of randomised trials has not identified any other relevant trials other than those cited in this protocol. A recent audit has demonstrated that despite increased investment and in number of linear accelerators, waiting times for radiotherapy have actually increased, thus highlighting the importance of critically evaluating fractionation schedules. The saving of 10 fractions per patients would for example

allow 6 patients with follicular NHL to receive palliative radiotherapy for the same linear accelerator resources as currently are required for one patient, or an additional 10 patients to be treated with palliative single doses for bone metastases in their place. Furthermore recent Ionising Radiation (Medical Exposure) Regulations 2000 (IRMER) have supported the need for all prescribers of radiation to critically appraise and justify each radiation exposure a patient receives.

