#### Treatment schedule

Treatment will be given over 16 days, treating daily Monday to Friday.

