#### Treatment schedule

Treatment will be given over 2 consecutive days.

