#### Secondary

Acute toxicity: assessed at the week 4 visit using RTOG Acute Radiation Morbidity Scoring Criteria

Late toxicity: assessed using RTOG/EORTC Late Radiation Morbidity Scoring Criteria or, if the RTOG criteria are not applicable, using the Common Terminology Criteria for Adverse Events v3.0 (CTCAE), available online at:

http://ctep.cancer.gov/protocolDevelopment/electronic\_applications/docs/ctcaev3.pdf

 $\underline{\textit{Response}}$ : assessed at the 12 weeks from randomisation using RECIST criteria

Overall survival: time from randomisation to date of death of any cause

Health economic assessment: details of protocol treatments, other anti-cancer treatments (excluding complementary therapy), management of adverse events, hospital admission episodes, and EQ-5D questionnaire

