#### **Acute Radiation Morbidity Scoring Criteria**

The RTOG acute radiation morbidity scoring criteria should be used to assess acute toxicity at visit 2 (4 weeks post randomisation)

	0	1 (expected for FoRT)	2 (expected for	(not expected for	4 (not expected for
SKIN	No change over baseline	Follicular, faint or dull erythema/ epilation/ dry dequamation/ decreased sweating	FoRT) Tender or bright erythema, patchy moist desquamation/ moderate edema	FoRT)  Confluent, moist desquamation other than skin folds, pitting edema	FoRT)  Ulceration, hemorrhage, necosis
MUCOUS MEMBRANE	No change over baseline	Injection / may experience mild pain not requiring analgesic	Patchy mucositis which may produce an inflammatory serosanguinitis discharge/ may experience moderate pain requiring analgesia	Confluent fibrinous mucositis/ may include severe pain requiring narcotic	Ulceration, hemorrhage or necrosis
EYE	No change	Mild conjunctivitis with or without scleral injection. Increased tearing	Moderate conjunctivitis with or without keratitis requiring steroids &/or antibiotics/ dry eye requiring artificial tears/ iritis with photophobia	Severe keratitis with corneal ulceration/ objective decrease in visual acuity or in visual fields/ acute glaucoma/ panopthalmitis	Loss of vision (unilateral or bilateral)
EAR	No change over baseline	Mild external otitis with erythema, pruritis, secondary to dry desquamation not requiring medication. Audiogram unchanged from baseline	Moderate external otitis requiring topical medication/ serious otitis medius/ hypoacusis on testing only	Severe external otitis with discharge or moist desquamation/ symptomatic hypoacusis/ tinnitus, not drug related	Deafness

	0	1	2	3	4
		(expected for FoRT)	(expected for FoRT)	(not expected for FoRT)	(not expected for FoRT)
SALIVARY GLAND	No change over baseline	Mild mouth dryness/ slightly thickened saliva/ may have slightly altered taste such as metallic taste/ these changes not reflected in alteration in baseline feeding behaviour, such as increased use of liquids with meals	Moderate to complete dryness/ thick, sticky saliva, markedly altered taste		Acute salivary gland necrosis

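### Acute toxicity is scored at one visit timed from randomisation, so with equal start delays the 4Gy arm is scored 14 days later after its last fraction than the 24Gy arm

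*Protocol*

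**What the plan says.** Acute toxicity is a listed secondary outcome. Three places in the protocol tie it to one visit:

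- Section 3.9: "Acute toxicity will be determined at 4 weeks post randomisation using the RTOG Acute Radiation Morbidity Scoring Schema".
- Section 5.2, secondary outcomes: "assessed at the week 4 visit using RTOG Acute Radiation Morbidity Scoring Criteria".
- Appendix 2, on the acute criteria: "should be used to assess acute toxicity at visit 2 (4 weeks post randomisation").

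The clock for that visit is set in section 1.2 (Duration): "All patient follow up visits are calculated from the date of randomisation". From visit 3, at 12 weeks, Appendix 2 switches to the late morbidity scale, so no second visit uses the acute scale.

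The courses differ in length. For the control arm (section 3.2): "Treatment will be given over 16 days, treating daily Monday to Friday". For the experimental arm (section 3.3): "Treatment will be given over 2 consecutive days".

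Section 5.4 compares toxicity between the arms by chi-squared or Mann-Whitney test.

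Three other places bear on the point. Figure 1 (section 1.3) shows treatment in weeks 1 to 3 and acute toxicity in week 4. Section 6 has all adverse events recorded from consent to the end of the trial, with onset and resolution dates, and graded by RTOG where possible. Table 4 (Appendix 4) requires the acute toxicity form at visit 2 only if the patient has had acute toxicity from radiotherapy.

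**The concern.** Acute reactions follow the irradiation, but the assessment is timed from randomisation. Because the courses differ in length, the interval between the end of treatment and the single score depends on the allocated arm. Randomisation does not balance such an offset, and a larger sample does not shrink it.

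What is at stake is the meaning of the comparison. If sites record only the reactions present at the visit, a 4Gy reaction has had two more weeks to settle than a 24Gy reaction. Part of any observed advantage for 4Gy could then reflect recovery time, not dose. The definition does not say whether the score is the state on the day or the worst grade so far, and sites could reasonably differ on this.

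**Working it through.** **Inputs**

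- Visit 2: 4 weeks = day 28 after randomisation (sections 1.2, 3.9, 5.2; Appendix 2).
- 24Gy arm: 12 fractions, Monday to Friday, over 16 days (sections 1.2, 3.2).
- 4Gy arm: 2 fractions over 2 consecutive days (sections 1.2, 3.3).
- Days from randomisation to first fraction, *d*: the text sets no limit. This is an assumption, shown over a range and taken as equal in the two arms.

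**Reproducing the stated 16 days.** From a Monday start, the 12 weekday fractions fall on days 1–5, 8–12 and 15–16, which is 16 days. Tuesday, Wednesday and Thursday starts also give 16. A Friday start gives 18, so the figures below use the stated 16 days and hence a Monday-to-Thursday start.

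**Formulas.** With the first fraction on day *d*:

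- last fraction, 24Gy: *d* + 15; days from then to visit 2: 28 − (*d* + 15) = 13 − *d*
- last fraction, 4Gy: *d* + 1; days from then to visit 2: 28 − (*d* + 1) = 27 − *d*
- difference: (27 − *d*) − (13 − *d*) = 14 days, whatever *d* is

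**Results**

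| First fraction, days after randomisation | 4Gy: days from last fraction to visit 2 | 24Gy: days from last fraction to visit 2 |
|---|---|---|
| 0 | 27 | 13 |
| 6 | 21 | 7 |
| 10 | 17 | 3 |
| 13 | 14 | 0 |
| 14 | 13 | −1 (last fraction still to come) |

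A start in the first week (*d* = 0 to 6) puts the score 21 to 27 days after the last fraction in the 4Gy arm and 7 to 13 days after it in the 24Gy arm. The 24Gy course is unfinished at visit 2 only if *d* is 14 or more.

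**Measured from the first fraction instead.** Visit 2 falls 28 − *d* days after the first fraction in both arms. A worst grade since the first fraction would therefore cover the same length of observation in each arm, which a grade on the day does not.

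**The case against.** The strongest reply is that little is lost in practice. Fixing the visit at 4 weeks may say only when the form is filled in, not that resolved reactions are ignored. Table 4 asks for the acute form if toxicity has been experienced, which can be read as covering the interval, and the guidelines in Appendix 2 make the acute criteria relevant from the first day of therapy. Section 6 separately captures every adverse event with dates and, where possible, an RTOG grade. Assessing both arms at a common time from randomisation is also a legitimate choice under intention to treat.

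Much of this stands. A reader might infer that resolved 4Gy reactions go unrecorded; section 6 shows that they should be in the notes and CRFs. What remains is that the outcome is defined by the week 4 assessment. No section makes it a worst grade or says that it draws on the adverse event records.

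A reader might also infer that many 24Gy patients will still be on treatment at visit 2. The protocol does not support that. Figure 1 has the 24Gy course over before the week 4 assessment. The remark in section 1.6 that "waiting times for radiotherapy have actually increased" comes from an audit cited to justify studying fractionation and gives no delay for this trial. A delay of 14 days or more is not excluded by the text, but nothing shows it to be common.

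Nor does the protocol present lower toxicity as a main argument for 4Gy. Sections 1.5 and 1.6 argue from efficacy and saved fractions, and section 1.7 claims only that no additional risk was identified.

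**Conclusion.** The point holds as a flaw in how a secondary outcome is defined. With equal start delays and the stated course lengths, the arms are scored 14 days apart relative to the end of treatment, and that gap is tied to allocation. Whether this biases the comparison depends on how sites read the form. If they score only what is present at the visit, the likely effect is to overstate the difference in favour of 4Gy. If some 24Gy courses were unfinished at the visit, the effect would run the other way, but that needs a first fraction 14 or more days after randomisation.

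The protocol gives no time course for reactions and no distribution of start delays, so the size of the bias is not known. The primary outcome is not touched. Importance is minor to moderate.

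**What to change.** In sections 3.9 and 5.2 and in Appendix 2, define acute toxicity as the worst RTOG acute grade for each organ since the first fraction. Record it at the existing visit 2, with the dates of first and last fraction, and supplement it with the RTOG-graded adverse event records already collected under section 6, over the same period from first fraction in both arms. Compare the arms on that grade.

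This needs no new visit. Its cost is a change of wording in the protocol and on the visit 2 form, and about 4 weeks of recall by patient and site. It lessens the timing problem without removing it: 24Gy patients still have less time after their last fraction by visit 2, which is why the adverse event records should be used as well.

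A repeat acute scoring at visit 3 is not needed. It would add an assessment beside the late scale and about 8 weeks of recall (12 − 4).

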#### 3.10 Other assessments

#### EQ-5D - Health Economic Assessment

The EQ-5D questionnaires (Appendix 1) should be completed without conferring with friends or relatives and all questions should be answered even if the patient feels them to be irrelevant. The appointed person at the site should check each questionnaire for its completeness, ensuring that the correct date of completion and patient identifiers are present.

A questionnaire is to be completed at every scheduled visit (see Appendix 5). The Research Nurse or delegated member of the clinical team should approach patients at appropriate clinical visits to complete a questionnaire. The completed questionnaire and coversheet should then be sent to UCL CTC.

## 3.11 Loss to follow up

Patients will be followed up for five years in the first instance and then for survival until death. If a patient fails to attend a clinic or can not be followed up at site, efforts should be made to contact the patient's GP to assess their condition. Any patients "lost to follow up" and who subsequently die will be "flagged" by the Office for National Statistics. The trial will also be registered with a number of cancer registries to enable follow up. This will be mentioned on the Patient Information Sheet.

## 3.12 Trial closure

The trial will be considered closed 5 years after the last patient is recruited. However, further observational follow up of all patients enrolled in the trial will continue until all randomised patients have died. This will initially be via the hospital, but in the longer term may employ national registers.

# 4. WITHDRAWAL OF PATIENTS

In consenting to the trial, patients are consenting to trial treatment, trial follow up and data collection.

# 4.1 Withdrawal from trial therapy

Patients may be withdrawn from treatment for any of the following reasons: -

- Disease progression within the irradiated field whilst on therapy/treatment
- ii. Patient withdraws consent
- iii. Unacceptable toxicity
- iv. Intercurrent illness, which prevents further treatment
- v. Any change in the patient's condition which justifies the discontinuation of treatment in the clinicians opinion

Data regarding a patient withdrawal prior to or during radiotherapy should be recorded on the Withdrawal From Treatment CRF. This form is only applicable for patients who either do not start, or fail to complete their randomised radiotherapy treatment. Patients who withdraw from the trial for other reasons have previously consented to follow up in the trial. If a patient wishes to withdraw from trial treatment, sites should nevertheless explain the importance of remaining on trial follow up, or failing this of allowing routine follow up data to be used for trial purposes.

### 4.2 Withdrawal from trial

If the patient explicitly states their wish not to contribute further data to the study, UCL CTC should be informed in writing (and a Withdrawal of Consent CRF should be completed). Data up to the date when the patient withdraws consent must be submitted. Patients may need to reaffirm that they consent to follow up through usual NHS mechanisms e.g. ONS.

#### 4.3 Patient transfers

For patients moving from the area, every effort should be made for the patient to be followed up at another participating trial site and for this new site to take over the responsibility for the patient. If it is not possible to transfer the patient's care to another participating site, the original recruiting site remains responsible for their follow up and should submit data based on copies of clinical correspondence from their new consultant or information obtained from the patient's GP (see section 3.11).

If a patient's follow up is transferred to another participating site, UCL CTC must be informed of the transfer in writing. The new site must be provided with a full copy of the patient's case report form, and the original site must submit all data up to the time their care was transferred. The patient will have to sign a new consent form at the new site, and until this occurs, the patient remains the responsibility of the original site.

# 5. STATISTICAL CONSIDERATIONS

#### 5.1 Method of Randomisation

Once written informed consent has been obtained, the completed registration and randomisation forms must be faxed to CR UK & UCL Cancer Trials Centre. Eligibility will be confirmed, and then the patient will be randomised. Randomisation will be at a 1:1 ratio and will be stratified by histology (follicular lymphoma vs. marginal zone lymphoma), and whether treatment is being given with curative or palliative intent.

#### 5.2 Outcome Measures

### **Primary**

Local progression free interval: time from randomisation to tumour progression **within the irradiated field** by clinical examination and imaging as appropriate for site of treatment and lymph nodes

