### 3.6 Measures of compliance and adherence

#### **Medications permitted**

All anti-cancer therapies (including complementary treatments/therapies) are permitted. Chemotherapy is allowed providing it is administered 4 weeks after the completion of radiotherapy.

Data on concomitant medication

All details of any anti-cancer treatments or therapies received (except complementary medications) are to be recorded on the Anti-Cancer Treatment CRF.

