# 7.2 Ethical approval

The protocol will be approved by the Cambridgeshire 4 Research Ethics Committee (formerly the Eastern MREC), and in addition Site Specific Approval must be obtained at each institution before patients are entered at that site.

The patient's consent to participate in the trial should be obtained after a full explanation has been given of the treatment options, including the conventional and generally accepted methods of treatment. Patients should be given sufficient time after being given the trial patient

information sheet to consider and discuss participation in the trial with friends and family. A contact number should be given to the patient should they wish to discuss any aspect of the trial. Following this, the randomising investigator should determine that the patient is fully informed of the trial and their participation, in accordance with ICH GCP guidelines. Patients should always be asked to sign a consent form. One copy should be given to the patient, one copy should be kept with patient's hospital notes and one copy should be kept in the local investigator's file.

The right of the patient to refuse to participate in the trial without giving reasons must be respected. After the patient has entered the trial, the investigator must remain free to give alternative treatment to that specified in the protocol, at any stage, if he/she feels it to be in the best interest of the patient. However, the reason for doing so should be recorded and the patient will remain within the trial for the purpose of follow up and data analysis according to the treatment option to which he/she has been allocated. Similarly, the patient must remain free to withdraw at any time from the protocol treatment without giving reasons and without prejudicing his/her further treatment.

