# **APPENDIX 4: FOLLOW UP SCHEDULE**

Table 3 shows the visit schedule for the FoRT trial

Table 3: FoRT trial visit schedule

Visit number	Timepoint
1	Baseline
2	4 weeks post randomisation
3	12 weeks post randomisation – response assessment
4	6 months post randomisation
5	1 year post randomisation
6	18 months post randomisation
7	2 years post randomisation
8	3 years post randomisation
9	4 years post randomisation
10	5 years post randomisation

Once the five years of scheduled follow up are completed, patients will be followed up for survival annually until death.

The forms due at each visit are summarised in table 4 below.

Table 4: Forms due at each clinic visit

Form	Details	Compulsory / as required
Registration form	4 pages to be completed at visit 1 and faxed to UCL CTC	Compulsory
Randomisation form	1 page to be completed at visit 1 and faxed to UCL CTC	Compulsory
4-week follow up form	1 page to be posted to UCL CTC within 8 weeks of visit 2	Compulsory
Acute toxicity form	1 page to be posted to UCL CTC to be completed at visit 2 as required and posted to the UCL CTC within 8 weeks of visit 2 along with 4-week follow up form	Only required if patient experienced acute toxicity from radiotherapy
12-week follow up form	4 pages to be posted to UCL CTC within 8 weeks of visit 3	Compulsory
Follow up form	1 page to be completed at visits 4 – 10 and posted to UCL CTC within 8 weeks of visit	Compulsory up to the point of local progression
Late toxicity form	1 page to be completed at visit 3 – 10 as required and posted to UCL CTC within 8 weeks of the relevant visit along with the follow up form	Only required if patient experienced late toxicity from radiotherapy
Disease progression form	1 page to be completed at first progression within the irradiated field	Only required at local progression
Disease progression follow up form	1 page to be completed at all scheduled visits after local progression instead of the follow up form	Compulsory after local progression
Anti-cancer treatment form	1 page to be completed at visits 2-10 as required and posted to UCL CTC within 8 weeks of the relevant visit along with the follow up form	Only required if patient received cancer treatment other than their trial radiotherapy
Hospital admission form	1 page to be completed at visits 2-10 as required and posted to UCL CTC within 8 weeks of the relevant visit along with the follow up form	Only required if patient is admitted to hospital

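### In-field re-treatment before progression is not a primary event; if it is commoner after 4Gy than after 24Gy, it can favour non-inferiority

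*Protocol*

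**What the plan says.** Section 5.2 of the protocol gives the primary endpoint as "time from randomisation to tumour progression" in the irradiated field, judged clinically and by imaging suited to the treated site. Re-treatment in the field is not listed as an event. Under the RECIST table in Appendix 3, partial response and stable disease are not progression.

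Section 3.6 states that "All anti-cancer therapies (including complementary treatments/therapies) are permitted". It then sets one limit: "Chemotherapy is allowed providing it is administered 4 weeks after the completion of radiotherapy". No limit is given for re-irradiation or for non-chemotherapy agents. Section 7.2 adds that "the investigator must remain free to give alternative treatment to that specified in the protocol, at any stage", and keeps such a patient in follow-up and in the analysis as allocated.

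The trial is open (section 1.2), and intention to treat is the only analysis named (section 5.4). Later therapy is documented: section 3.8 asks that "any subsequent treatment for lymphoma at any anatomical site should be recorded", and section 3.6 and Appendix 4 provide an Anti-Cancer Treatment form. In Appendix 4 the routine follow-up form is "Compulsory up to the point of local progression", so re-treatment alone does not end observation of the field.

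**The concern.** Read together, these rules class a patient whose residual or stable in-field disease is re-treated as still free of local progression. The new treatment may then delay or prevent the progression that would have been counted.

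An excess after 4Gy is plausible. In the 4Gy series cited in section 1.5, 61% of sites had a complete response, which leaves 39% without one. Clinicians know which patients had the lower dose. For palliative patients, section 3.8 leaves imaging to clinical indication, so re-treatment without documented progression can happen.

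In a superiority trial, losing failures from the experimental arm would call for care. In a non-inferiority trial it moves the result directly towards the claim.

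**Working it through.** **Inputs from the protocol.** Section 5.3 and Table 2: 2-year rate 50% in control and 40% at the margin, hazard ratio 1.32, one-sided 5%, 90% power, 4 years of accrual, 1 year of follow-up, 446 events, 671 patients, planned total 650. Section 5.1: 1:1 allocation.

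**Step 1: reproduce Table 2.** Schoenfeld events = 4 × (1.645 + 1.282)² / (ln 1.32)² = 445. Freedman's formula at the exact ratio ln 0.4 / ln 0.5 = 1.322 gives 446. With exponential times, λ = −ln(2-year rate)/2, so λ = 0.347 in control and 0.458 at the margin. With uniform accrual, the event probability is 1 − (e^(−λ) − e^(−5λ))/(4λ), which is 0.617 and 0.710, mean 0.664. Then 445/0.664 to 446/0.664 gives 670 to 672 patients. The stated 446 and 671 are reproduced and are not in dispute.

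**Step 2: expected failures at 650 patients with the truth at the margin.** Control: 325 × 0.617 = 201. 4Gy: 325 × 0.710 = 231. Total about 431 before rounding of the arms.

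**Step 3: hide some failures.** Let fE and fC be the shares of would-be in-field failures in the 4Gy and 24Gy arms that are re-treated first and never counted. These shares are assumptions.

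- Observed HR = 1.322 × (1 − fE)/(1 − fC)
- dE = 231 × (1 − fE), dC = 201 × (1 − fC), SE = √(1/dE + 1/dC)
- P(non-inferiority declared) = Φ[(ln 1.322 − ln HR observed)/SE − 1.645]

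Example with fE = 5% and fC = 0: dE = 219, dC = 201, SE = 0.098, HR = 1.256. The shift is 0.051/0.098 = 0.525, and Φ(0.525 − 1.645) = 0.13.

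| Hidden share 4Gy / 24Gy | Events | Observed HR | P(false non-inferiority) |
|---|---|---|---|
| 0% / 0% | 431 | 1.322 | 5% |
| 10% / 10% | 388 | 1.322 | 5% |
| 5% / 0% | 420 | 1.256 | 13% |
| 10% / 5% | 398 | 1.252 | 13% |
| 10% / 0% | 408 | 1.190 | 28% |
| 15% / 5% | 387 | 1.183 | 29% |
| 20% / 10% | 365 | 1.175 | 30% |
| 20% / 0% | 385 | 1.058 | 71% |

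The difference between arms drives the result. Five per cent of 231 failures is about 12 patients. The last row is an extreme case, not an estimate.

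**Limit of the model.** It lets a re-treated patient leave the risk set when progression would have occurred. The protocol keeps such patients under observation. Simulating them as still at risk and never progressing did not shrink the effect of an arm difference. Equal shares then no longer hold the error exactly at 5%, because both curves are diluted, but that shift is smaller than the one from a 5-point arm difference.

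**The case against.** The definition in section 5.2 is a normal one for local control. Sections 5.4 and 7.2 and Appendix 4 together follow re-treated patients on and count them if they later progress in the field. That is a recognisable treatment-policy approach, and censoring rules and sensitivity analyses are usually left to the SAP, which is not at hand.

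This stands in part. The absence of such SAP detail is no fault in the protocol. But the protocol itself fixes the primary event. An SAP that keeps that definition can only follow patients through re-treatment or censor them at it. If re-treatment reflects poor control and is commoner after 4Gy, both lean the same way.

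A reader might infer more than the documents support:

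- **That the trial is biased.** This needs more pre-progression in-field re-treatment after 4Gy. No rate is given for either arm.
- **That the direction is certain.** Knowing that a patient had 4Gy could also lead to earlier calls of progression, which works against non-inferiority. An uncontrolled opposite bias is no safeguard, but the net direction is unknown.
- **That further therapy is unrestricted.** Chemotherapy has the 4-week limit.
- **That week-12 response is equally undermined.** If radiotherapy starts at randomisation, the chemotherapy limit passes at about day 2 + 28 = 30 or day 16 + 28 = 44, both before day 84. But the rule is the same in both arms, no rate of early chemotherapy is given, and response is secondary. Its handling belongs in the SAP.

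**Conclusion.** The point holds as a conditional risk. As written, the endpoint treats in-field re-treatment before progression as a non-event, and the protocol permits such re-treatment in an open non-inferiority trial. If the share of failures hidden this way is 5 points higher after 4Gy, the false non-inferiority rate is about 13% instead of 5%; at 10 points it is about 28–30%.

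These figures assume a true hazard ratio at the margin, exponential times, 650 patients, a test on the hazard-ratio scale, and hidden shares chosen for illustration. They show how sensitive the claim is to modest asymmetry and are not evidence that asymmetry will occur. The change is worth making because it is cheap, but the trial does not depend on it.

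**What to change.** In sections 5.2 and 5.4, count in-field re-irradiation before documented progression as a local failure at the date it starts. Preferably do this in the primary endpoint. At minimum, make it a pre-specified key sensitivity analysis that must agree with the primary result before non-inferiority is claimed.

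Add a further sensitivity analysis that also counts systemic anti-lymphoma therapy started before in-field progression as an event. This is better kept out of the primary definition: why systemic therapy was started is an open-label judgement, and the protocol does not show that the forms capture it.

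Confirm that the Anti-Cancer Treatment form records the anatomical site and whether treatment was aimed at in-field or out-of-field disease.

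Cost: endpoint and analysis wording, and possibly one form field, since later treatment is already recorded. A few re-treated patients who would never have progressed will count as failures. If they are mainly in the 4Gy arm, that works against the non-inferiority claim, the cautious direction here. No change to patient care is implied.
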